All outcomes in this study will be assessed at 90 days (3 months) post randomization, and all efforts will be made to ascertain outcomes at this point in time. Because this is a pragmatic study and there are no study visits, participants will also complete a visit which will coincide with a regularly scheduled standard of care follow-up visit approximately 3 months post randomization at which point study outcomes will be assessed. If participants are unable to return to the clinic they may be contacted to complete the 3 month follow up visit via phone call, email, or mail. If a patient completes the follow up visit prior to the 3 month anniversary, a medical record review will be conducted in order to assess for potential outcomes that were not recorded at the premature follow up visit. To fully assess for any missed outcomes, the research coordinator may assess for potential events in the patient's medical record..

At the time of the 3 month follow up visit (in-person or virtual), participants will be interviewed by the Research Coordinator to assess for the occurrence of any clinical outcomes, including VTE events or complications secondary to treatment since their hospitalization. For each event identified, the participant will fill out a release of information form that will allow the research staff to obtain records related to the event, if they occurred outside the index facility. Participants A Randomized Pragmatic Trial Comparing the Complications and Safety of Blood Clot Prevention Medicines Used in Orthopaedic Trauma Patients Version 11.0 6/1/2021 23

The PREVENT CLOT study protocol is the confidential intellectual property of the PREVENT CLOT Principal Investigators, Steering Committee, and the University of Maryland Baltimore and METRC and cannot be used in any form without the expressed permission of the Principal Investigators.

will be asked about study medication satisfaction using the Treatment Satisfaction Questionnaire for Medication (TSQM)³¹ and about their total out of pockets costs related to obtaining the study assigned medication. Additionally, the medical record will be carefully reviewed to assess for any complications treated at the index facility, including in the clinic, ED, or resulting in a rehospitalization.

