As stated above, due to the potential affects that COVID-19 has on patients, ie increased risk of clotting, COVID-19 status will be recorded if available via medical record review also at follow up. Research team member will record whether the patient is experiencing any symptoms related to COVID-19 or has tested positive. This data will be collected on all patients who have enrolled into the study since January 2020.

Lost to follow up participants

A percentage of participants will fall in the category where they cannot be contacted, do not return to clinic, or return to clinic but do not have 90 days of follow-up. Additional contact methods will be used to verify these participants' death status which is critical for determining the primary outcome, all-cause mortality. The following methods, which are also described in more detail below, will be used to assess outcomes on these individuals: (1) medical record review, (2) postcard questionnaire, (3) phone call or text follow up from coordinator (4) search via LexisNexis Accurint system, (5) phone call and text message follow up from MCC, (6) search via Limited Access Death Master File (LADMF)

Medical Record Review

If the participant cannot be contacted and does not return for a final research visit, medical records will be abstracted through the last orthopaedic encounter occurring between anytime from the last clinical encounter to the time of medical record review. The visit occurring closest to the 3 month follow-up target should be recorded(e.g. for a participant seen at 60 days, 185 days and 400 days, the 60 day visit should be recorded to demonstrate use of services in the follow-up interval, and the 185 day visit should be recorded to demonstrate that the participant was alive and free of any orthopaedic events at 185 days and therefore also alive and event-free at 90 days, the date of interest. No other visit data should be recorded. Attempts will be made to obtain medical records or autopsy reports for all participants who are discovered to be deceased at the time of the follow up visit. If the participant died at home, family members will be asked to provide a cause of death, if known. No attempts will be made to follow up with family, and the deaths will be recorded as "unknown" cause.

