If a patient cannot be contacted AND has no evidence of returning for any orthopaedic clinical visit, the medical record will be searched for any evidence of an encounter with the medical system documenting that the patient survived through at least 3 months post randomization. If the encounter occurred before 3 month post randomization information, information related to study outcomes available at the encounter. If the encounter occurs anytime following the 3 month post randomization date the date and visit type will be recorded. The resulting information

The PREVENT CLOT study protocol is the confidential intellectual property of the PREVENT CLOT Principal Investigators, Steering Committee, and the University of Maryland Baltimore and METRC and cannot be used in any form without the expressed permission of the Principal Investigators.

will provide evidence that the patient was alive during the window of interest, allowing ascertainment of information on the primary outcome.

Postcard questionnaire

Each lost to follow up participant will receive a one-time pre-stamped postcard questionnaire requesting information on the participant's death status. The postcard will be addressed to the participant however may be returned by a family member, friend, or resident of the participant's home. Sample of this postcard is in Attachment H.

To facilitate centralized distribution and retrieval of these cards, clinical sites will send the patient's full name and mailing address, along with the study ID number, to the MCC using a secure, encrypted, password-protected File Transfer Protocol. The MCC will centrally send out postcards using an automated postcard development and mailing electronic service.

Phone call/text message follow up (Research Coordinator)

Research coordinators will call the participant or emergency contact listed in the participant's medical record or social work/case management file to determine the participant's death status. This phone call will be in addition to any attempts made during the follow up period. If the Research Coordinator gets in contact with the patient a full follow up visit and questionnaire will be conducted. If the Research Coordinator can only determine the participant's death status based on conversations with the family and/or emergency contact the death status will be recorded. Sample of the text message/call script is in Attachment I.

Search via LexisNexis Accurint Services

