The MCC will obtain identifiers such as but not limited to the patient's name, date of birth, social security number, and last known address using a secure, encrypted, password-protected File Transfer Protocol. The identifier will be used to conduct probabilistic mapping through public and proprietary database search. Any identifiers will aid in specialized mapping of this database will be used in the search, and the database will return up to date mailing and phone contact information for the participant, as well as any publicly reported deaths.

Phone call/text message follow up (Centralized through MCC)

The MCC will centrally contact each participant and emergency contact, when necessary to evaluate the death status of the participant using the contact phone numbers previously provided by participating centers for weekly follow up as well as information obtained from the Accurint search. Clinical sites may also obtain any additional phone numbers associated with the participant's medical record and transfer it, along with the study ID number, to the MCC using a secure, encrypted, password-protected File Transfer Protocol. All statues will be saved in REDCap. Sample of the text message/call script is in Attachment I.

Search via Limited Access Death Master File (LADMF)

The PREVENT CLOT study protocol is the confidential intellectual property of the PREVENT CLOT Principal Investigators, Steering Committee, and the University of Maryland Baltimore and METRC and cannot be used in any form without the expressed permission of the Principal Investigators.

There will be a subset of patients who cannot be contacted AND have no evidence of any further encounters with the clinical system. For these cases, ascertaining final death status is critical to the validity of the study, and the study team has developed a plan to allow sites to obtain this information while conforming to local policies regarding the sharing of PHI and accessing available data. Because this study is being executed in 21 trauma centers, including 2 centers in Canada, the method for determining if a patient passed away during the study interval will vary. Local IRBs will review the protocol and make a determination regarding if and how this information will be obtained, according to the following options:

- A. Sites have the option to send a secure, encrypted password-protected LOOK-UP File to the MCC for a centralized database search of the Limited Access Death Master File (LADMF).

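### Unreachable patients with an orthopaedic visit get a narrower chart review than patients who never returned, so non-fatal events before day 90 can go unrecorded; the death-search trigger is also inconsistent

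*Combined protocol and SAP*

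**What the plan says.** References are to protocol version 11.0 unless the SAP is named.

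Section 6.3.1 counts as lost those who cannot be contacted, those who do not come back, and those who "return to clinic but do not have 90 days of follow-up". It lists six methods for them: record review, postcard, coordinator call or text, LexisNexis Accurint search, central call or text, and the Limited Access Death Master File (LADMF). The lead-in is "The following methods, which are also described in more detail below, will be used to assess outcomes on these individuals".

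The detailed rules then differ by type of patient:

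- **Unreachable, no final research visit, some orthopaedic visit:** "medical records will be abstracted through the last orthopaedic encounter", and "The visit occurring closest to the 3 month follow-up target should be recorded". In the example, a patient seen on days 60, 185 and 400 has the first two visits recorded. Freedom from orthopaedic events at day 185 is taken to mean event-free at day 90. Then: "No other visit data should be recorded".
- **Unreachable, no orthopaedic visit:** "If a patient cannot be contacted AND has no evidence of returning for any orthopaedic clinical visit, the medical record will be searched" for any encounter with the medical system. Outcome information is evidently wanted from encounters before 3 months.
- **Follow-up visit completed:** "the medical record will be carefully reviewed to assess for any complications treated at the index facility, including in the clinic, ED", and readmissions. If that visit was completed before 3 months, a further record review is required.
- **LADMF:** the subsection opens with "There will be a subset of patients who cannot be contacted AND have no evidence of any further encounters with the clinical system". Its Option A text refers once to wholly lost patients. Elsewhere it covers every lost patient whose death status is unknown.

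SAP section 3 calls for record review to find any documented clinical or research contact after the last study visit, and ends follow-up at that contact if it falls before day 90. Section 10.3 expects no missing outcome data for death or clinically significant PE.

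**The concern.** The rules rank patients in the wrong order. Someone who never returned to orthopaedics has the whole record searched. Someone who completed follow-up has clinic, ED and readmissions reviewed. Someone with one early orthopaedic visit, who then cannot be reached, has that visit recorded and nothing more. A PE diagnosed in the ED of the same hospital on day 30 lies outside the review written for that patient.

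At stake are the secondary estimands for non-fatal PE, DVT and bleeding (SAP sections 7.3.3 and 7.3.4, estimands 5 to 7), which are defined on events observed by day 90. Vital status is at stake to a lesser degree, because the text does not say consistently who enters the death-file search. Section 6.3.1 itself calls that search critical to the study's validity.

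**Working it through.** The point rests mainly on wording, so the first step applies the rules to four patients, none of whom can be reached except the completer.

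| Patient | Chart review as written | LADMF search |
|---|---|---|
| No orthopaedic visit, no other encounter | Whole record | Yes |
| Orthopaedic visit on day 30 only | That visit | No, if a further encounter means any after discharge; yes, if it means any after last contact, or under the lead-in or the wider Option A text |
| Orthopaedic visits on days 60 and 185 | Those two visits | Not needed: known alive at day 90 |
| Follow-up visit completed | Clinic, ED, readmissions | Not needed if completed at or after day 90 |

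**Non-fatal events.** In rows two and three, a PE, DVT or bleed treated by another service before day 90 need not be recorded. The postcard and central call ask about death status, and Accurint returns contact details and reported deaths. Only reaching the patient leads to a full follow-up interview. The review required after an early visit applies to a completed follow-up visit, not to a routine orthopaedic one.

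**Handling in the SAP.** The row-two patient is censored at last contact (SAP sections 3 and 7.3). The row-three patient has contact beyond day 90, so an unrecorded event is carried as 90 days without that event.

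**The plan's own figure, for context.** Section 10.1 states more than 95% power at 1% mortality in both arms with a 0.75-point margin. With 6,100 per arm, a 96.2% two-sided interval (z = 2.075) and interim looks ignored:

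- SE = √(2 × 0.01 × 0.99 / 6,100) = 0.00180
- Power = Φ(0.0075/0.00180 − 2.075) = 98.2%

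The statement is reproduced.

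**Illustrative size for deaths.** Section 10.1 gives 12,200 patients, 1% mortality and 7.5% attrition; the attrition figure belongs to the calculation for the former primary outcome. Assumptions, not in the documents: one third to two thirds of lost patients have only an early orthopaedic visit, and their mortality is 1% to 3%.

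- Lost: 0.075 × 12,200 = 915
- In the gap: 915/3 = 305 to 2 × 915/3 = 610
- Deaths at 1%: 3.1 to 6.1
- Deaths at 3%: 9.2 to 18.3
- All expected deaths: 0.01 × 12,200 = 122

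These are upper figures for the assumed inputs. Some of these deaths would be found by postcard, calls or Accurint, or by LADMF on the wider reading. With wider assumptions (25% to 100% of lost patients, 1% to 5% mortality), 229 to 915 patients and about 2 to 46 deaths are exposed. The documents give no figure for how many patients resemble row three.

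**The case against.** A reader might infer that these patients get no death-file search, that their deaths are therefore missed, and that the trial is pushed towards non-inferiority. The documents do not support that chain.

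- The lead-in in section 6.3.1 names this very patient and applies all six methods, LADMF included. The wider Option A text agrees, and SAP section 7.1 lists death registries without any visit condition. Exclusion is one reading of one opening sentence.
- The postcard, both calls and Accurint carry no condition on orthopaedic visits, and Accurint returns publicly reported deaths. The most that can be said is that a death could be missed.
- The SAP censors lost patients. If missed deaths were counted as survivors, and 5% were missed equally in both arms at 1% versus 1.75%, the chance of declaring non-inferiority would rise from 1.9% to 2.9%. That is not the planned analysis. Under Kaplan-Meier, bias needs informative censoring. That is possible, since a survivor with a later visit is carried to day 90 while an unfound decedent stops at an early contact. How far it would happen is not derivable.

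It can also be argued that the bar on other visit data closes an example and was meant only to drop the day-400 visit. Section 10.3 asks sites to fill missing data from medical records, section 6.3.1 permits a record check for missed outcomes, and section 6.2.1 captures index-admission events separately. This softens the point but does not remove it. Abstraction is still tied to orthopaedic encounters, and the whole-record search is still conditional on there being none. General encouragement elsewhere does not override a specific instruction to coordinators.

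**Conclusion.** The point holds for non-fatal outcomes. As written, an unreachable patient with an orthopaedic visit gets a narrower chart review than either a patient who never returned or one who completed follow-up. A PE, DVT or bleed charted by another service before day 90 can go unrecorded. A later visit does not cure this, because freedom from orthopaedic events is not freedom from events treated elsewhere. The rule affects estimands 5 to 7 and sits badly with SAP section 3 and with the expectation in section 10.3 of complete data on clinically significant PE.

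For deaths the defect is a contradiction to be reconciled. A death before day 90 could be missed in a patient with only an early visit if a site applies the narrow LADMF wording and the postcard, calls and Accurint all fail. Mortality would then be biased only if that censoring is informative. Neither direction nor size follows from the documents. The 3 to 18 deaths out of about 122 illustrate the exposed group under assumed shares and risks; they do not estimate deaths lost. This should be corrected, but it does not by itself undermine the primary analysis.

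**What to change.** 1. For every patient without a completed 90-day follow-up, including those with a later visit, review the whole index-facility record (clinic, ED, readmissions, non-orthopaedic care) from randomization through day 90, and record every study outcome with its date. Delete the bar on other visit data, or limit it to visits that add nothing on outcomes through day 90. Remove the condition that the whole-record search applies only when there was no orthopaedic visit.
2. Reconcile the lead-in, the LADMF opening and the Option A text of section 6.3.1 into one trigger. The LADMF or local death search, at sites using Option A or B, should cover every patient not known to be dead and without documented contact on or after day 90, whether or not an earlier encounter exists.

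The cost is protocol wording, modest coordinator time for extra chart abstraction, and a longer look-up file for a search already planned. Sites already do the same abstraction for patients who complete follow-up.

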6.3.2 Retention

Every effort will be made to retain participants in the study. The study participants will receive an honorarium in recognition of their time and effort. \$20 will be given for completing the 3 month visit in appreciation for their time and effort. Participants who complete follow-up activities by phone or email will be given \$20 for competing the interview. We will also keep participants engaged through use of study updates on the study webpage and distribution of follow-up reminders, which can include mailings and e-mails.

7. STUDY TREATMENTS

Patients meeting inclusion/exclusion criteria will be prospectively randomized to one of two treatment arms using the REDCap Database randomization tool embedded. Block randomization with variable block sizes will be used.

7.1 Study Treatments

7.1.1 Description of treatment

The PREVENT CLOT study protocol is the confidential intellectual property of the PREVENT CLOT Principal Investigators, Steering Committee, and the University of Maryland Baltimore and METRC and cannot be used in any form without the expressed permission of the Principal Investigators.

Study Treatment 1: LMWH is currently an accepted medication used to prevent blood clots after trauma, and it is supported by existing guidelines so it is already in widespread use through the United States.^{9,10} Enoxaparin is available from multiple manufacturers; local site purchasing will determine the product received by the patient. Clear guidelines already exist regarding dosing in very obese patients as well as in patients with renal disease.^{35,36} The LMWH intervention is expected to be 30 mg enoxaparin SC twice a day which is already standard in many trauma hospitals. The protocol for this pragmatic trial will allow for variations in dosing, per the standard of care at sites, as needed for patients who are very obese or exhibit renal dysfunction. These variances will be recorded to allow them to be identified in the data.

Study Treatment 2: Aspirin is currently regarded as an accepted medication to prevent blood clots after orthopaedic surgery, is supported by existing guidelines³⁷ and is already in widespread use in the United States. Aspirin is less commonly used in trauma although it has gained significant popularity in the orthopaedic arthroplasty (joint replacement) domain.^{22,23,27} Aspirin was chosen as the comparative intervention because it is thought to have an excellent complication profile (low rates of bleeding and chronic wound drainage) and still to be effective in preventing blood clots in the lung, although these data are in joint replacement patients.^{22,23,27,37} Aspirin works by effecting platelets irreversibly and this effect typically lasts 7 days, which is a potentially important difference from the shorter acting LMWH. The advantage of a shorter acting medication is that the effect can be turned off easily when the patient needs additional surgery or if a contraindication for bleeding develops. A down side is that missed doses with LMWH quickly place the patient with no blood clot prevention. Aspirin is typically continued even when surgeries are performed so the fact that aspirin cannot be “reversed” is likely not important in this domain, but the importance of this effect in trauma patients is unknown.

The dose of aspirin for this study is not obvious as several reported doses have been used successfully. Options include 81 mg once a day, 81 mg twice a day, 180 mg once a day, 325 mg once a day, and 325 mg twice a day. The desired effect of reducing the risk of clots is thought to occur at the 81 mg dose once a day and many joint replacement surgeons use this dose to prevent blood clots.³⁸ Anti-inflammatory effects are thought to become more pronounced as the dose increases and some of the original joint replacement studies used 325 mg twice a day. We believe that lower doses may be desirable in trauma as it likely reduces the chance of bleeding from other traumatic injuries and it is not necessarily desirable to have the anti-inflammatory effects of higher doses, as anti-inflammatory medicines have been linked to delayed bone healing in animal models.³⁹ We therefore have chosen 81 mg twice a day as it represents a dose towards the lower end of the dosing spectrum and gives twice a day dosing, similar to LMWH, decreasing the chance of patients missing a dose for the whole day. Further, a study of geriatric hip fractures,²¹ which is as close to our population as has been studied for this question, successfully used 160 mg once a day.

7.1.2 Investigational Drug Status

The PREVENT CLOT study protocol is the confidential intellectual property of the PREVENT CLOT Principal Investigators, Steering Committee, and the University of Maryland Baltimore and METRC and cannot be used in any form without the expressed permission of the Principal Investigators.

Both study treatments are FDA approved medications that are commonly used for the indication proposed in this application; however only LMWH has this listed as an approved indication in its product labelling. ASA for this indication is “off label” for use as DVT prophylaxis. In accordance with 21 CFR 312.2, this study meets IND Exemption requirements. An application for an IND exemption was approved by the FDA for the proposed indications outlined in this protocol. The intention of the protocol is not to support a new indication for use or significant change in labeling of the drugs; is not intended to support a change in advertising for the drugs; will not test a new route of administration or dosage of the drug, nor is it being used in a new clinical population; and the study will be conducted with informed consent and in compliance with 21 CFR 312.7 regarding promotion and sale of drugs. Patients in the study will be actively monitored for any adverse reactions.

For patients enrolled at Canadian sites, the in-patient administration of ASA and the ASA prescribed to the study participant at their discharge will be dispensed by the treating hospital’s pharmacy. As per the labelling standards of the Food and Drug Regulations (C.05.011) labels for the ASA, in both English and French, will be included with each administered dose. The label will state that the ASA is for clinical trial use only, the name and identifying mark of the drug, the expiration date of the drug, the recommended storage conditions for the drug, the lot number for the drug, the protocol code “PREVENT CLOT”, and the name of the sponsor (R Adams Cowley Shock Trauma Center, University of Maryland, [name]).

